#### **4. Research Risks**

The prosthetic knees have hydraulics and sensors. This type of device is classified as a prosthetic component and is a FDA Class I device. This means that it is a low-risk type of medical equipment. Although these procedures are very safe and commonly used in our lab, participation in this study may involve the following risks: The primary risk of injury in this protocol would be due to falls, regardless of the prosthesis being used. To minimize this risk, participants will be asked to wear a safety harness and initially walk with handrails until they become comfortable using the prosthetic device(s) and demonstrate that they can use it without falling. Should participants fall during this familiarization session, the harness will support them. When walking overground, participants will still have the option of wearing the safety harness, access to hand rails or other walking aids, and may be supported by staff members using a gait belt as you complete the activities. When participants wear the prosthesis at home, they will not have access to a harness or gait belt. This is similar to what happens in clinical scenarios when a prosthetist fits a patient with a prosthetic component; while in the clinic, familiarization occurs and then the patient is sent home to use the device independently.

A second risk is muscle soreness and fatigue. Muscle soreness is a common

problem when walking with a new prosthesis. To prevent this, experimental sessions will be kept as short as possible, adequate rest periods will be provided between trials, and participants will be questioned often about any discomfort.

A third risk is skin irritation. Skin can become irritated while using any prosthesis and it may also become irritated by adhesive reflective markers. Additionally, the residual limb will be checked prior to and after the study to inspect for skin irritation or if participants experience discomfort in their residual limb during the study, we will give time for the socket to be removed to allow for appropriate inspection. To avoid the risk of skin irritation, participants will use your normal, take-home socket.

A fourth risk is that participants may find that they prefer a different prosthetic knee following use of the various knees within the study and may not be able to obtain this knee through your clinical provider and/or insurer. We will provide all information to you that you request regarding your performance in the various knees but the goal of the study is not to provide participants with a knee to take home following the study.

## **5. Confidentiality**

Participants will sign a consent form before participating which explains that no identifiers linking them to this study will be included in any sort of report that might be published except for the video taken. Participant faces will be blocked out upon request. They will be given a pseudonym different from their own name that will be referred to in studies published, if at all. Participants will be assured in the informed consent that the data will be used only for studies that are consistent with the original research purpose.

This consent form will be filed securely in an official area. People who have access to information include the Principal Investigators and research study personnel. Representatives of regulatory agencies such as the Office of Human Research Protections (OHRP), the Food and Drug Administration, the DoD, and entities such as the Georgia Tech Office of Research Integrity Assurance may access participant records to make sure the study is being run correctly and that information is collected properly.

Information about participants related to this study will be kept confidential to the extent permitted or required by law.

When the data is stored, it will no longer be linked to the subject's personal information. There will be a master list stored separately that connects the subject identifiers with their personal information, for when they need to be contacted. The data will be kept on the computers of the research personnel only. These computers will all be password protected to prevent non-authorized access to the data. Data will be transmitted electronically between researchers. The master list of subjects and their personal information will not be transmitted in any form between researchers. This master list will only be in the possession of the PI and researcher responsible for recruiting. It will not be shared with anyone else in any way.

## **6. Benefits**

Our goal is to optimize the prosthetic prescription process for currently available

MPK devices as there is no current understanding for which MPKs are best suited for which patients. The long-term goal of this research is to improve the ability of people with amputations to be able to walk better and more easily: including walking on level surfaces, stairs, ramps, hills and other activities.

## **7. Compensation**

Subjects will be paid at \$20/hour while they are in the lab and an addition \$300 once they complete the full study to incentivize all subjects to complete the full study which is important for our results. Free parking will be provided to all subjects when they come to campus for experimental sessions.

Subjects will be given the choice of compensation via check which will be issued through USPS mail to their home (or a provided) mailing address or a gift card which will be provided at the end of each visit to the lab.

## **8. Costs**

There are no direct costs to study participants. The costs to participants for this study will most likely be only their time and energy. Participants will be responsible for covering any unforeseen costs including, but not limited to, transportation to the research location, parking expenses, food, or child care.

## **9. Alternatives**

Participants are informed that participation in this study is voluntary. It is made clear that they have the right to change their mind and leave the study at any time without giving any reason and without penalty. Any new information that may make participants change their minds about being in this study will be given to them.

## **10. Consent/Accent Process and Documentation of Consent/Accent**

After being informed about the study through recruitment by way of flyers, e-mail or word of mouth, participants will be given a consent form outlining details about the study. The consent form provides detailed information about the study procedures. When reading through the consent form potential participants are encouraged to vocalize any questions they have including, but not limited to, inquiries about testing procedure, risks of the study and participant rights. Questions will be answered by the researcher personnel conducting the study. Participants will be given as much time as they need to make a decision about whether or not to participate. During this process, as well as throughout testing it will be made clear that participants may choose to end the study at any time, no questions asked, and will not face any negative repercussions. Signing of the consent form will take place in person where researchers present will answer any questions then obtain their signatures. This consent form will be filed securely in an official area, that can only be accessed by Principal Investigators of this study and research study personnel. Participants will be given a copy of this consent form and do not waive any legal rights by signing it.

The only personal information we will collect is the participant's name, telephone, email, and contact information. This information will not be published in the research results, nor will it be used to perform data analysis. This information will also not influence the

results of the research. We only collect this information so we can contact the participants and refer to them by their names during conversation.

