4. Acclimation time varies widely in the literature (from 3-10 hours [2, 3] to months [4]) and is acknowledged to have important implications for this study's results. In this study, subjects will go through an initial tuning and training process similar to what is done in clinic scenarios including tuning knee parameters and training over the various terrains in the lab including stairs, ramps and a treadmill. Subjects will then proceed to wear the prosthesis for 1 week at home and in the community in order to acclimate to the device and then return to the lab for testing. A sensor to collect data about the number of steps participants take will be attached to the prosthesis and/or your shoes. This sensor does not have a GPS and will not record where subjects go. Subjects will use their same socket, prosthetic foot and shoe during each knee evaluation to ensure that differences observed during the study are attributable to the knee.
5. Subjects will ambulate five times over the 18' instrumented gait mat to determine their self-selected walking speed (SSWS) and GVI. Subjects will complete a 2-minute walk test and then be administered the Borg RPE.[5] A heart rate monitor will be worn during the 2 minute walk test in order to calculate physiological cost index (PCI) [6]
6. Subjects will proceed to walk up and down an overground 5-degree ramp for ten trials and then walk up/down a 6-step stair case for ten trials while we measure lower body 3D biomechanics and completion speed.

7. Subjects will walk across a beam while wearing the prosthesis. The beam is very low in height and sits only ~2" inches off the ground.
8. Subjects will walk on a treadmill while wearing the prosthesis while we measure lower body 3D biomechanics.
9. Subjects will then fill out the OPUS HRQOL, LEFS, PEQ, Veteran SF-36, and fall history survey to assess their perception of performance and other health related quality of life factors associated with use of each device. Pilot work with these surveys indicates this will take approximately 30-45 minutes.
10. Subjects will repeat Steps 4-8 with periods of rest provided as necessary until they have completed the full protocol for each of the three MPKs and research grade powered knee.

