During all testing participants are instructed to vocalize any concerns or discomfort to researchers. Tests that occur in the lab will occur with the use of a safety harness and or gait belt. During tests, verbal feedback from the participants will be used to improve the comfort of the devices. Participants are instructed to notify researchers if they feel unsafe, and may quit the study at any time without penalty. Additionally, participants may be asked to wear EMG sensors, markers for measuring biomechanics and other mechanical sensors (such as IMUs) All participants will be guided through the following general procedure during their visits, requiring action on their part:

- Participants will be briefed about the details of and their rights during the study.
- The prosthesis and attachment interface will be fit to the participant, along with any additional data collection equipment.
- Participants will be guided through the specific activities of the study, detailed already.
- Participants will receive assistance removing any sensors used during the study.

Other equipment may be utilized to measure biomechanics of the user during ambulation. Specifically, we will be using a VICON motion capture analysis system and an instrumented treadmill. This will also us to measure biomechanical similarities and differences while using the powered prosthesis compared to the sound side limb. Also, some protocols will require the use of an EMG (electromyography) system to measure muscle activity across different ambulation tasks. Three systems may be used which includes the Delsys Trigno Wireless EMG system, Biometrics Ltd. EMG system, and COAPT EMG system. All of these systems will use electromyography sensors that will be placed on the surface of the user's skin.

In order to also measure functional clinical measures, a Protokinetics gait mat will be utilized to measure common measures such as step length, step time, and symmetry. This system is just a mat that users will need to walk on top similar to walking overground. Users will be in a harness and have the options for handrails or gait belt if needed.

Throughout the tests there will be a camera recording the session. The purpose of the camera is to record performance for future analysis. The participant will always have the right to stop the test and/or take a break. The participant may also choose to discontinue participation at any time.

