During the first visit, fitting and tuning will be no longer than 4 hours. Participants may end the visit at any time without penalty, or choose not to return for additional visits. If the participant agrees to continue the study subsequent visits will be scheduled at their convenience and pending availability of the prosthetic knee joints. During these subsequent visits, testing will last between 2-6 hours based on participant comfort.

Participants will be asked to attend at least 5 sessions in order to compare the effectiveness of the different prosthetic knees. However, each participant will maintain the right to discontinue their involvement for future sessions. Depending on the progress of the tests, participants may be involved in sessions ranging over the course of a few months.

The results of the study will be in the form of device performance and participant feedback. Sensor data will record the movement parameters of the subject. This includes mechanical instruments on the device and biomechanical instruments attached to both the device and the human subjects. These instruments will give information about the kinematics (movement), kinetics (force), muscle activity, step count, heart rate and metabolics of the user. This allows for the effectiveness of the design strategy to be assessed. The participants will also give feedback in the form of verbal conversation. This verbal feedback will deal with the comfort, convenience and preferences of the devices and controllers.

This study will use statistical analysis to compare between different intent recognition systems. We will use intent recognition accuracy as the primary metric to compare statistical differences across conditions. We will compare biomechanics between the powered device and a passive prosthesis. Typically, ANOVA tests are used with repeated measures to compare across multiple conditions.

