### Statistical & data analysis plan

A repeated measures ANOVA with within factor MPK will be used to assess differences across treatment for Aims 1 and 2, provided assumptions are met. In the event of missing data or violation, a linear mixed models procedure, which does not assume compound symmetry, will be considered. Bonferroni-Holmes correction will be made to control for family-wise error rate. Samples size calculations are outlined below. Estimated effect size was calculated using Cohen's d for within factor designs [71], assuming a correlation among repeated measures of 0.5. Effect sizes were then converted to Cohen's f for sample size estimations using G\*Power. [72] **Aim 1: Comparison of clinical outcome measures on MPKs.** A Borg RPE of 2 (pooled SD= 2) was deemed clinically relevant for this study, resulting in an effect size of 1. Gait variability index effect size was based upon minimally detectable change (MDC) cited in [73]. An MDC of 8 and hypothesized pooled SD of 6, produced an effect size of 1.3. These data indicate a sample size of approximately 9 will achieve 90% power. The sample size proposed in this study (N=12) should ensure adequate power, even in the event of attrition or slightly higher variability. **Aim 2: Patient reported outcomes.** Resnik & Borgia (2011) have suggested a MDC of 10.3 (90% CI) for OPUS lower limb function.[61] Effect size for this study was calculated using MDC of 10 and a pooled SD of 7.7, assuming higher variability than previously reported SD's for upper

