## **11. Investigator's Qualifications**

The PI, [name], has conducted a number of experiments similar to this one with amputees. The Co-PI, [name], is a certified prosthetist specifically trained to work with individuals with amputation and fit prosthetic devices to them. Three of the prosthetic knees used in this protocol are clinically available through manufacturers and used broadly in the prosthetics clinical community. These are the devices that will be brought home for 1 week testing protocols with participants. The fourth device is our own experimental investigational device and the testing of this device was IRB approved previously at Georgia Tech with a separate, but related protocol. All members listed on this IRB protocol have CITI training.

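### A take-home knee given up during its home week yields none of the step 5 to 9 outcomes, and the plan neither records the rejection nor treats it as informative

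*Combined protocol and SAP*

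**What the plan says.** **Timing of outcomes (Section 3, step 4).** After tuning and training, "Subjects will then proceed to wear the prosthesis for 1 week at home and in the community", and then come back for testing. The gait mat, 2-minute walk, Borg rating, ramp, stairs, beam, treadmill and questionnaires (steps 5 to 9) all follow that return.

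**Sequence (Section 3, step 10).** The cycle is repeated "until they have completed the full protocol for each of the three MPKs and research grade powered knee".

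**Which knees go home (Section 11).** Of the three commercial knees it says: "These are the devices that will be brought home for 1 week testing protocols with participants". The powered knee is not included, although steps 4 and 10 read as if all four have a home week.

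**Rights to stop.** Section 3 says "The participant will always have the right to stop the test and/or take a break" and "Participants may end the visit at any time without penalty, or choose not to return for additional visits". Sections 9 and 10 add the right to leave the study; in the words of Section 10, "participants may choose to end the study at any time, no questions asked, and will not face any negative repercussions". None of these mentions giving up one knee, how that is recorded, or what it means for the analysis.

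**Data during the home week (Section 3, step 4).** "A sensor to collect data about the number of steps participants take will be attached to the prosthesis and/or your shoes". Section 3 also lists verbal feedback on comfort and preference among the results.

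**Analysis (Statistical & data analysis plan).** "In the event of missing data or violation, a linear mixed models procedure, which does not assume compound symmetry, will be considered". Aim 3 leaves the model to be chosen later and does not list rejection of a knee among its outcomes.

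**The concern.** The objective is to match a knee to a person. A participant who hands a knee back after three days has given about the clearest evidence of a mismatch that the study can obtain. Followed as written, the plan has no value for that knee on any named outcome and treats the gap as ordinary missing data.

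A mixed model handles missingness that the observed data explain. Here the cell is empty because the result would have been poor, and that result is the one not seen. The likely direction is that a poorly tolerated knee looks better in Aims 1 and 2 than it is, and that the Aim 3 algorithm does not learn from the rejection. The situation is foreseeable: Section 4 names falls as the primary risk and notes that home wear has no harness or gait belt.

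**Working it through.** **1. The plan's own figure.** For a within-subject ANOVA, λ = f²·N·m/(1−ρ) with m−1 and (N−1)(m−1) degrees of freedom. Take m = 4 knees, ρ = 0.5 (stated), f = d/2, sphericity and α = 0.05 (assumed; not stated).
- Borg: d = 2/2 = 1, f = 0.5, λ = 0.25·9·4/0.5 = 18, power 92.2% at N = 9 (87.7% at 8).
- PEQ: d = 1.1/1.25 = 0.88, f = 0.44, λ = 0.1936·9·4/0.5 = 13.9, power 83.4% at N = 9 (77.4% at 8).

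Both stated sample sizes of 9 reproduce. The margin for attrition (12 in the analysis plan; the goal is 17 in Sections 1 and 2) buys precision. Bias from selective loss is not removed by a larger N.

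**2. Size of the bias, by simulation.** From the plan: Borg SD 2, correlation 0.5, a difference of 2 points, 17 participants, four knees in random order. Assumed: three knees have equal means and one is 2 points worse; a participant leaves when the score on the current knee passes a threshold (4.0 or 3.5 above the mean of the better knees). The estimand is the worse knee minus the average of the others. The mixed model is represented by generalised least squares with the true covariance.

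| Setting (all assumed) | Mixed model | Complete cases |
|---|---|---|
| No loss | about 2.0 | about 2.0 |
| About 3 leave, exit set by the score itself | 1.73 | 1.78 |
| About 4.5 leave, same mechanism | 1.64 | 1.70 |
| About 1 leaves, same mechanism | 1.87 | |
| About 3 leave, reason correlates 0.5 with the score | 1.84 | |
| About 3 leave, reason correlates 0.3 with the score | 1.91 | |
| Threshold 4.0, only the rejected knee is missing, others completed | 1.68 to 1.70 | |

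With about 3 leaving, the shortfall is 2.00 − 1.73 = 0.27, or 0.27/2.00 = 13.5%. The standard error with full data is √[4·(1−0.5)·(1+1/3)/17] = 0.40, so the bias is about 0.27/0.40 = 0.7 of a standard error.

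The last row matters for the remedy. Continuing with the other knees cuts lost person-knee cells from about 12–13% to 6%, but does not reduce the bias, because the informative value is still absent.

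**3. A more selective mechanism, with a hand check.** Let every rejection fall on the poor knee and come from its lowest scorers, in SD units with a true deficit of 1.00. For complete cases the bias is (1−ρ)·φ(z)/(1−p). With p = 3/17 = 0.176, z = −0.93 and φ(z) = 0.259, this is 0.5·0.259/0.824 = 0.157, so the deficit shrinks to 0.84. Simulation also gives 0.84, and 0.77 for a likelihood analysis (0.92 with 1 rejection of 17, 0.62 with 5). On the Borg scale, 0.77·2 = 1.54.

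**4. What early collection recovers.** If the rejected knee's own Borg score is obtained, the estimate returns to about 2.0, provided the early score equals the full-week score. Borg is a step 5 measure, taken after the 2-minute walk. The step 9 questionnaires alone do not supply it.

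**The case against.** The strongest reply is that the documents are silent, not restrictive. A reader might infer that leaving the whole study is the only exit, so that a participant must either keep wearing a bad knee or withdraw. The documents do not support this: Section 3 also allows stopping a test, ending a visit or not returning, and nothing forbids an early return or moving on to the next knee.

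Nor is it right that a rejected knee leaves no data. Step counts and verbal feedback exist; they are just not tied to any analysis of rejection. The timing point is certain only for the three commercial knees. The promise that no questions are asked protects withdrawal and does not bar recording a reason that a participant volunteers. It also goes too far to say that Aim 3 would be trained only on people who tolerated every knee: a mixed model keeps the earlier knees of those who leave, and the Aim 3 model is still open and exploratory.

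On size, the plan gives no exit rate, the threshold mechanism is extreme, the $300 completion payment encourages people to stay, and the main bias is below one standard error at N = 17.

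All of that stands and limits the strength of the point. It does not answer the core: no rule ensures that rejection is captured, and the one missing-data provision does not cover missingness caused by the knee.

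**Conclusion.** The point holds as a cheap improvement, not as a fatal flaw. For the three commercial knees, giving up a knee in the home week leaves all step 5 to 9 outcomes missing. The analysis plan would treat that as ignorable, and Aim 3 does not use it.

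Under an assumed 3 exits of 17 driven directly by the score, a 2.0-point Borg difference is estimated at about 1.73. Fewer exits or a weaker link give about 1.84 to 1.91; rejections confined to the lowest scorers on the poor knee could take it to about 1.54. The direction, towards flattering the poorly tolerated knee, is the same throughout. The size rests on exit rates and mechanisms that the documents do not give.

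A reader might infer that handing out questionnaires at early return makes the bias disappear. That is not shown: it would hold only for outcomes actually collected, and only if early scores match full-week scores.

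**What to change.** Amend Section 3 and the analysis plan as follows.

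- **(a) Collection.** When a knee is returned early, for whatever reason, offer the step 9 questionnaires and fall history for that knee, and record the date and an optional reason. Also offer the step 5 measures if the participant and clinicians consider that appropriate; without them the Aim 1 bias is not corrected.
- **(b) Aims 1 and 2.** Keep these values in the main analysis, flagged by wear time. Add one sensitivity analysis for outcomes not obtained: give the rejected knee that participant's worst rank (tied if there is more than one) and use a rank-based within-subject test, such as Friedman, or Skillings–Mack where other cells are empty. State beforehand which early returns count as rejection, including those with no reason given.
- **(c) Aim 3.** Enter rejection as an observed outcome, not suitable for this person, instead of as missing.
- **(d) Reconciliation.** Reconcile step 10, which expects the full protocol for every knee, with the stopping rights in Sections 3, 9 and 10, and steps 4 and 10 with Section 11 on which knees go home. Step 10 also repeats only steps 4 to 8; include step 9 by name. Whether and when a participant stops a knee or goes on to the next is for the participant and clinicians.

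**Cost.** A short amendment, 30 to 45 minutes of existing questionnaires per early return (more if step 5 is done), and one extra analysis. The downside is that early-return scores reflect less wear than full-week scores, which is why the wear-time flag is needed.
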